7.3. Randomisation by Internet and Telephone

Patients will be randomised after written informed consent has been obtained in the outpatient clinic, at pre-operative assessment or on admission for surgery.

Randomisation will be performed by a member of the ROCSS team at the site. The person undertaking randomisation or operating surgeon receiving the randomisation allocation should have no involvement in the post-operative assessment of the patient.

Patients are entered into the trial either by internet on the secure website: https://www.trials.bham.ac.uk/ROCSS or by a telephone call to the randomisation service ([name]) at the University of Birmingham Clinical Trials Unit (BCTU).

Telephone randomisation is only available Monday-Friday 0900-1700 UK time, but the secure internet-based randomisation is available 24 hours a day. These methods, which are both managed by BCTU, will ensure concealment of randomised treatment allocation. Each centre and each

randomiser will be provided with a unique log-in and password to enable them to access the online randomisation service.

Randomisation Notepads are provided in the ROCSS site file and should be used to collate the necessary information prior to randomisation. After all the necessary details have been provided, the treatment allocation will be specified and the patient will be assigned a unique trial identification number to be used on all trial related material for the patient.

The operating surgeon, assistant and theatre team will be aware of the randomised treatment allocation, but the patient and post-surgical wound assessor will remain blind to treatment allocation.

7.4. Randomisation Method

Participants will be randomised into the ROCSS trial in a 1:1 ratio of mesh reinforcement to control (standard closure without mesh). A 'minimisation' procedure using a computer-based algorithm will be used to avoid chance imbalances in important prognostic variables.

The minimisation variables will be:

- 1. Stoma type ileostomy versus colostomy.
- If stoma involves an ileostomy and colostomy, it will be stratified into the colostomy group as the current literature shows that colostomies are at a higher risk of hernia than ileostomy¹¹.
- 2. Surgical incision reopening of midline wound or stoma site only.
- 3. Skin closure type primary or secondary.

8. Treatment and Follow-Up

Please see Appendix B for a detailed patient pathway for the day of surgery.

8.1. All Patients

Prophylactic antibiotics will be given to all patients according to local protocols. The ileostomy or colostomy (including bowel, fascia and skin) will be closed in accordance with the surgeon's preferred technique (i.e. stapled or hand sewn).

Immediately after closure of bowel, the size of the fascial defect should be measured before its closure. The size should be recorded as the length of the longest dimension measured. The presence of midline hernias will also be recorded, as will be whether they were repaired with separate mesh or not.

8.2. Experimental Arm – Reinforcement by Collagen Mesh

A standardised technique has been recommended by the steering committee surgeons. This has been developed and filmed and documented. In order to standardise this experimental arm, the following measures will be taken:

- 1. Technique DVD and instructional, illustrated paper will be distributed to the local Principal Investigator (PI).
- 2. A member of the Trial Management Group will offer to visit the site to assist the PI during the initial procedure. The PI should normally have performed a minimum of 20 previous stoma closures.
- 3. Local PIs will be asked to disseminate the technique to other participating surgeons within their hospital.
- 4. As further centres open, workshops will be made available to participating surgeons to review the technique.
- 5. Local PIs will be able to attend theatre of the trial PI during a case if they wish.

The protocol preference is for the mesh to be placed intra-peritoneally fashion (i.e. below the peritoneum). Anchoring bites will be taken in four to six sites of peritoneum (e.g. using 2-0 PDS) and the mesh will be 'parachuted' into place. Once correctly placed, the fascia above will be closed using Prolene, PDS or Nylon (surgeon preference, but excluding Vicryl). Infiltration of up to 40ml 0.25% Marcaine for infiltration into the fascial layer is recommended. The remainder of the closure will be at the surgeon's discretion.

8.3. Strattice® Mesh

Biologic meshes are sterile tissue matrices which are derived from animal tissues. The main cellular component of the tissues is removed, leaving behind a matrix upon which the patient's own tissues can grow. Since they are not formed from prosthetic material, the risk of infection when used in contaminated situations is much lower. These biologic meshes are strong, compatible with the patient's tissues and will eventually be incorporated into the patient's own tissues.

Strattice® is a popular type of biologic mesh and is in use for other indications, such as difficult abdominal wall reconstruction. It is derived from porcine dermis and once the cellular component is removed, it is packed under sterile conditions. It has already been used in parastomal hernia repair and open abdominal wall repair, but has not been used during stomas site closure as proposed by ROCSS.

The Strattice® mesh to be used within the trial is CE marked and the license includes use with abdominal wall reconstruction, hernia and hernia repair.

Indications for use

Biologic meshes (such as Strattice®) are used to reinforce soft tissue where weakness exists and for the surgical repair of damaged or ruptured soft tissue. Indications for use include the repair of hernias and/or body wall defects. This includes its use as a bridging material to obtain closure. However its use as a prophylactic mesh to prevent hernia formation in complex and contained wounds has not been fully assessed. ROCSS provides such a model to test this type of mesh in a randomised fashion. The mesh should be prepared according to manufacturer's instructions, which include washing with saline prior to implantation.

Contraindications

This biologic mesh is derived from a porcine source and should therefore not be used in patients with known sensitivity to porcine material. Patients who object to the implantation of a porcine derived mesh may decline to consent. However, since there is no cellular component and the mesh is implanted rather than ingested, some of these patients may not object and so participation should still be offered.

8.4. The Control Arm – Established Technique

The ileostomy or colostomy will be closed in accordance with the surgeon's preferred technique, which will typically involve a handsewn or stapled bowel closure.

The non-intervention arm for fascial closure will be the preferred technique of the surgeon without mesh reinforcement. In order to provide standardisation of this arm, the following technique will be recommended:

- 1. The surgeon should normally have performed a minimum of 20 stoma closures.
- 2. The fascia should be closed with Prolene, PDS or nylon sutures; Vicryl should not be used for the fascia. This technique can include either interrupted or continuous sutures.
- 3. Closure of the muscle, soft tissues and skin is up to the discretion of the operating surgeon.

8.5. Compatibility with Other Studies

Patients in other colorectal cancer trials are eligible for ROCSS if the other trial does not deal with surgical technique. ROCSS would not be compatible with neo-adjuvant colorectal cancer trials such as FOxTROT. Patients where there is potential conflict should only be approached to enter the ROCSS trial after discussion with the Trial Management Group via the ROCSS Trial Office.

9. Assessment Schedule

ROCSS

Both the patient and the medical and nursing staff responsible for the follow-up assessments will be blinded as to whether or not the stoma closure has been reinforced with collagen mesh.

Trial data will be recorded by hospital research staff on the Case Report Forms (CRFs) and submitted to the ROCSS Trial Office at the BCTU. The patient's unique trial number, initials, hospital number and date of birth will be recorded on all proformas.

Data will be collected at patient entry, intraoperatively, 30-days post-operatively and at 12 and 24 months post randomisation. This is summarised in the table below.

	Prior to patient entry/ Day of admission for surgery	At surgery	30 days post-op +/-5 days	12 months +/- 3 m	24 months +/- 1 m
Informed consent					
Clinical examination			V	\checkmark	
Pre-operative assessment data	\checkmark				
Operative details					
Clinical follow-up				\checkmark	\checkmark
Complications			V	\checkmark	\checkmark
Re-interventions			V		\checkmark
Resource usage (Cost collection)				\checkmark	
Quality of Life & Pain Measures			\checkmark		
CT scan					

At the time of patient entry into the trial, the following data will be collected:

- Demographics (age, gender, BMI, primary indication for stoma, when stoma was formed, diabetes, steroid medication)
- Type of stoma to be closed (ileostomy, colostomy)
- Parastomal hernia
- Incisional midline hernia from primary surgery
- Quality of life forms and pain visual analogue scale.

9.1. Treatment Evaluation

- Technique used either reinforced with collagen mesh (Strattice®) or not
- Post-operative complications (e.g. ileus, wound infection, chest infection)
- Duration of post-operative stay
- Development of hernia as judged clinically at 12 and 24 months post-randomisation
- Development of hernia as judged radiologically at 12 months post-randomisation
- Any re-operations will be recorded along with their indications (e.g. herniation, infection of mesh).
- Quality of life forms and pain visual analogue scale at 30 days post-operation, 12 months and 24 months post-randomisation.

Operative data will be recorded at time of surgery. Post-operative complications will be recorded on the 30-day Post-Operative Follow-up form.

The patients should be contacted by telephone by the research team at site prior to both of the 12 and 24 months review to remind them about their upcoming follow-up assessment and CT scan (if applicable) at 12 and 24 months. The research team at site will be provided with guidance on what should be discussed during reminder telephone calls.

At 12 and 24 months post-randomisation, Follow-up forms will be used to collect information on the presence of clinical hernia and re-intervention rates this may be done in real time or as a last resort from clinics attended within the follow up time frame (+/- windows for the visit).

A radiological assessment of the presence of hernia will be completed at 12-months postrandomisation. Quality of Life and pain forms should be completed at randomisation and then at 30 days post-operatively and 12 and 24 months post-randomisation.

10.Clinical Follow-up

ROCSS

10.1. Clinical Follow-Up Visits

Patients will be seen at 30 days post-op (+/- 5 days) to assess wound healing and surgical complications. Patients will then be reviewed at 12 months post-randomisation (+/- 3 months) for radiological and clinical assessment, with a final clinical assessment at 24 months post-randomisation (+/- 1 month). Any other follow-up will be at the discretion of the clinical team.

Follow-up clinical assessments will be performed by a surgeon, qualified to MRCS level or above. This should be standard practice however in cases where a MRCS level is not possible, a surgeon with MRCS equivalent or a nurse who has completed a physical examination course as part of a masters degree or similar may undertake the clinical examination.

MRCS equivalence and nurse qualification is assessed by the local PI and demonstrated by the delegation of the clinical examination duty.

Clinical examination assessors are to be blinded to the randomised allocation."

Below is the recommended standardised clinical examination technique for the closed stoma site.

Clinical examination

- 1. The patient should be examined according to this scheme in both standing and lying positions.
- 2. The patient should perform either a Valsalva manoeuvre or a forceful cough, whilst the placing of a hand over the closed stoma site.
- 3. You should record if the patient has:
 - a. A palpable fascial defect with or without protrusion of bowel or fat;
 - b. A global weakness around the stoma scar, without palpable fascial defect.
- 4. If in doubt, a second blinded clinician should be consulted and consensus achieved.

Definition of a hernia

For this study, a clinical hernia is defined as a palpable or visible discrete protrusion at the site of the stoma closure, possibly with a palpable fascial defect. A clinically global weakness is defined as a palpable or visible generalised weakness/ protrusion, which takes on no discrete nature and where no

fascial defect is palpable. A radiological hernia is defined as any breach in the abdominal wall muscles or fascia visible on CT scan, with or without the passage of bowel, omentum or fat through it.

This study will include optional consent to allow future linkage to patient data available in NHS routine clinical datasets, including primary care data (e.g. CPRD, THIN, QResearch), secondary care data (Hospital Episode Statistics; HES) and mortality data from the Office of National Statistics (ONS) through The Health and Social Care Information Centre and other central UK NHS bodies. The consent will also allow access to other new central UK NHS databases that will appear in the future. This will allow us to extend the follow-up of patients in the trial and collect long-term outcome and health resource usage data without needing further contact with the study participants. This is important as it will link a trial of a treatment that may become a clinical standard of care to long-term outcomes that are routinely collected in clinical data, but which will not be collected during the follow-up of patient of the trial.

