10.2. Twelve Month Post-Operative CT Scan

One of the secondary outcome measures in ROCSS is the presence of a hernia on CT scan at 12 months post randomisation. For these purposes, a hernia will be defined as any evidence of a defect present in the abdominal wall (see above: Definition of a hernia). A time frame of +/- 3 months from this 12 month time point is acceptable.

It is expected that the majority of trial participants will have had a stoma for colorectal cancer. In this group of patients, a one year post-operative abdominal/pelvic CT scan to assess for cancer recurrence is routine in the UK. This CT scan will be performed as a standard CT scan of the abdomen and pelvis as per the participating hospital's local protocol using a maximum slice thickness of 5mm. This routine scan will be used to assess for hernia recurrence instead of arranging a study one-year post-randomisation scan. In exceptional cases, an MRI scan as per participant's hospital local protocol may also be used to assess for hernia recurrence for patients undergoing surgery for cancer.

Non-cancer patients who have a stoma for a benign condition (such as Crohn's disease) usually do not routinely require CT follow up. These patients thus need an additional CT scan at one year to assess for hernia recurrence. This CT can be performed in one of the following two ways:

- 1. **Standard low dose CT KUB protocol**: (to detect renal tract calculi) using no oral contrast, no IV contrast and a maximum slice thickness of 5mm, so enabling a lower radiation dose exposure.
- 2. Limited CT scan protocol: For those patients who are having a CT scan that would not normally be performed (i.e. a stoma originally placed for benign disease) a local centre may choose to follow a low radiation dose protocol. This should be performed as follows:
 - i. No IV or oral contrast is required.
 - ii. Instead patient drinks 1L of water over 45 minutes (flavoured if desired).
 - iii. Low dose scan (same as the local institution's CT-KUB protocol).
 - iv. Stoma site identified visually on the skin and a marker placed (e.g. a thin paper clip).
 - v. Scout scan of abdomen performed.
 - vi. This is used to plan the axial slices in which a block 10cm above and 10cm below the skin marker (but no lower than pubic symphysis) is acquired. This is to take into account that the skin closure site may not correspond to the abdominal muscle closure site, particularly in obese trial participants).

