10.3. Ultrasound Sub-study

One of the secondary outcome measures in this study is to evaluate the detection rate of stoma site hernias with a CT scan at one year. This CT is performed as a 'standard' scan, in a supine position with the patient holding their breath. It is possible that this CT scan will not detect abdominal wall hernia owing to the lack of a 'dynamic' element. In order to address this concern, we propose using ultrasound to scan 40 consecutive patients who have undergone their one year follow-up CT scan in the Queen Elizabeth Hospital Birmingham as part of the ROCSS trial.

This sub-study is described in detail in the sub-study protocol that can be found in the appendices.

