Appendix C: Radiology Sub Study Protocol

Sub-study Protocol:

Ultrasound versus Computed Tomography detection of hernia

Background

Hernias can be detected in many ways. These include measures reported by patients, those detected by clinicians, and those detected by imaging methods¹⁻³. This has led to uncertainty about which is the best method to use for reporting randomised trials. Since hernias can take many years to become apparent, clinical detection is time-consuming⁴. Surrogate imaging markers may provide earlier delivery of endpoints. This would rely on reliability and reproducibility of imaging modalities, which would need to be clearly correlated with clinical endpoints. Within these controversies, it is unclear if ultrasound (USS) or computed tomography (CT) imaging is the best modality.

One of the secondary endpoints in the ROCSS study is to evaluate the detection rate of stoma site hernias with a CT scan one year after the closure of the stoma. This CT is performed as a 'standard' scan, in a supine position with the patient holding their breath. It is possible that this CT scan will not detect abdominal wall hernia owing to the lack of a 'dynamic' element. In order to address this concern we propose using ultrasound to scan 40 consecutive patients who have undergone their one year follow up CT scan in the Queen Elizabeth Hospital as part of the ROCSS trial. This ultrasound will be performed in a standardised manner corresponding to the standardised clinical examination. We will aim to perform the ultrasound at the same time the patient attends for their CT scan so that they only need to attend the hospital on one occasion. The radiologist will perform the ultrasound examination prior to any review of the CT scan.

Aims

To compare the efficacy of ultrasound versus computed tomography detection of hernia.

Research Questions

What is the correlation between ultrasound detected and computed tomography detected herniation?

- 1. Does USS or CT detected hernia correlate to a higher degree with clinical detection of hernias?
- 2. Does USS or CT detected hernia correlate to a higher degree of patient reported hernia?

Design

Recruitment and Consent

Access to participants will be through the Queen Elizabeth Hospital (University Hospital Birmingham NHS Foundation Trust) and through the ROCSS trial with ethical and local R&D approval. Potential participants will be identified by the relevant consultant and researcher.

Sampling

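### As written, the CT hernia definition names no site and would count any abdominal wall breach, which conflicts with the protocol's own description of the outcome as stoma site hernia

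*Protocol*

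**What the plan says.** Section 10.1 gives two definitions in one paragraph. The clinical one has a location: "a clinical hernia is defined as a palpable or visible discrete protrusion at the site of the stoma closure". The CT one does not: "A radiological hernia is defined as any breach in the abdominal wall muscles or fascia visible on CT scan". Section 10.2 restates the rule for the 12-month scan, again without a location, and refers back to 10.1: "For these purposes, a hernia will be defined as any evidence of a defect present in the abdominal wall".

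Elsewhere the same secondary outcome is described as site-specific. Section 10.3 says the aim is to "evaluate the detection rate of stoma site hernias with a CT scan at one year", and Appendix C to "evaluate the detection rate of stoma site hernias with a CT scan one year after the closure of the stoma". The ultrasound definition in Appendix C also requires the defect to lie where the stoma was closed.

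The protocol expects hernias at other sites. Section 9 lists "Incisional midline hernia from primary surgery" among the entry data. Section 8.1 records midline hernias at surgery and whether a separate mesh was used. Reopening the midline is a minimisation variable (7.4). No section says how a midline hernia seen on the 1-year CT is classified.

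**The concern.** Someone applying the definition and someone applying the description would classify the same scan differently. Under the definition, a patient with a sound closure site and a midline hernia is CT-positive. Under 10.3 and Appendix C, that patient is not.

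Three uses of CT status depend on this.

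- **The 1-year comparison.** Radiological hernia is the first-listed secondary outcome (section 5) and is analysed like the primary (13.2). Defects that closure-site mesh cannot prevent would add events to both arms.
- **CT as an early marker (13.3).** A CT-positive, clinically negative patient is a false positive. A breach elsewhere, set against an examination of the closure site, would be a spurious one.
- **ROCSS-EX (19.7).** The exploratory quality-of-life comparisons group patients by clinical or radiological hernia. A patient whose closure site is intact could enter the hernia group.

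Under an any-site rule the chance of being an event also depends on the scan. Cancer patients have the whole abdomen and pelvis imaged. Patients with benign disease have either a low-dose CT KUB or, if the centre chooses, a block 10 cm either side of the stoma marker, which the radiographer may extend.

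**Working it through.** **1. The plan's own figure.** Section 13.1: 25% versus 15%, two-sided alpha 0.05. With pooled variance and no continuity correction,

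n per arm = [1.960·√(2·0.20·0.80) + z·√(0.25·0.75 + 0.15·0.85)]² / 0.10²

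- 80% power (z = 0.842): (1.1087 + 0.4724)² / 0.01 = 250 per arm, 500 in total.
- 90% power (z = 1.282): (1.1087 + 0.7193)² / 0.01 = 335 per arm (rounded up), 670 in total.

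Both match the protocol. That calculation is for the clinical outcome; section 13.1 gives no separate size for the CT outcome.

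**2. What an any-site rule does to the comparison.** The Protocol Summary reports 455 scans (229 and 226), about 228 per arm. Let p be the closure-site rate and q the rate of defects elsewhere, taken as equal in both arms and independent of closure-site hernia. The documents give no value for q, so it is an assumption shown over a range. The rate counted is 1 − (1 − p)(1 − q).

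| q | Control | Mesh | RR | Power |
|---|---|---|---|---|
| 0 | 25.0% | 15.0% | 0.60 | 76% |
| 2% | 1 − 0.75·0.98 = 26.5% | 1 − 0.85·0.98 = 16.7% | 0.63 | 72% |
| 5% | 1 − 0.75·0.95 = 28.75% | 1 − 0.85·0.95 = 19.25% | 0.67 | 66% |

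**3. What the reported result allows.** Reported: mesh 20/229 = 8.7%, control 47/226 = 20.8%, crude RR 0.42. If these totals include defects elsewhere, q in the mesh arm cannot exceed 8.7%, and a value near that leaves almost no closure-site hernias there. Removing q from the reported totals, site-only rate = (reported − q)/(1 − q):

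| q | Mesh | Control | RR |
|---|---|---|---|
| 0 | 8.7% | 20.8% | 0.42 |
| 2% | 6.9% | 19.2% | 0.36 |
| 4% | 4.9% | 17.5% | 0.28 |
| 8% | 0.8% | 13.9% | 0.06 |

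Under equal counting the site-only effect would be larger than reported, not smaller.

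**4. What it could do to 13.3 and 19.7.** There are 20 + 47 = 67 CT-positive patients.

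- q = 2%: site-only positives are 0.0687·229 + 0.1918·226 = 59.1, so about 8 of 67 would be positive only because of a defect elsewhere.
- q = 4%: 0.0493·229 + 0.1750·226 = 50.8, so about 16 of 67.

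These patients would be CT-positive with a sound closure site. They are spurious false positives in 13.3 if the closure site stays clinically clear, and wrongly grouped in 19.7.

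**The case against.** The context points to the stoma site. The primary objective (4.1) concerns stoma closure site hernias, and 10.3 and Appendix C name the site for this very outcome. The limited scan is centred on the stoma marker, and the protocol explains the size of the block by where the muscle was closed. The CT sentence in 10.1 can be read as saying that no hernia contents are needed, rather than as saying that location is irrelevant. Two blinded central radiologists complete a standard form, which may restrict the site.

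The reported figures show no sign of heavy dilution. The CT control rate (20.8%) is close to the clinical control rate (64/327 = 19.6%), and the CT RR (0.42) is further from 1 than the clinical RR (0.62). The 1-year comparison is already published with p<0.001. Scan type follows the disease indication, which is fixed before randomisation, so it does not favour an arm. In ROCSS-EX the hernia groups serve exploratory comparisons only.

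All of this stands, and it limits the size of the problem. It does not remove it. The two operative definitions agree with each other and both omit the site. The sentences that name the site describe the outcome in a sub-study and are not case definitions. An unseen form does not correct a definition that the protocol states twice.

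A reader might infer that midline and other hernias were in fact counted, or that the published CT result is unreliable. The documents support neither. The form is not shown, and equal counting would bias toward no difference.

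**Conclusion.** The definition is incomplete and contradicts the protocol's own description of the outcome. Followed literally, it misclassifies midline hernias that the protocol expects to occur.

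The cost to the 1-year comparison is modest at plausible rates: an RR of 0.63–0.67 instead of 0.60, and power of 72%–66% instead of 76%, for q of 2% to 5%. These figures assume that q is equal in both arms and independent of closure-site hernia, and q itself is not in the documents. The reported mesh-arm rate rules out a realised q much above 8%. Under the same assumptions the ambiguity cannot have produced the reported benefit.

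What can still be put right is the reading of CT against clinical findings (13.3) and the ROCSS-EX hernia groups (19.7). The randomised primary comparison in ROCSS-EX does not use CT status and is unaffected.

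**What to change.** - In 10.1 and 10.2, limit the CT definition to the stoma closure site, using the site wording that the clinical definition already has.
- State that defects elsewhere (midline, groin, other) are recorded as a separate item and do not count towards the outcome.
- Use site-specific CT status for the 13.3 comparison and for the hernia groups in 19.7.
- If the reading form did not record location, confirm it from the stored reads for the 67 reported CT-positive scans. Report any resulting change to the published 1-year comparison as a sensitivity analysis, and do not replace the published result.

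The cost is one phrase in two places and one recording rule, with no new scans. If location was not recorded, there is also a small amount of re-checking.
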